The information gathered in this study may help the patients and physicians determine the best treatment options in the future. The experience of participating in this study may also help other patients benefit from improved diabetes management learned by patients and investigational staff using the MiniMed 640G System. Furthermore, results from this study may address potential device and clinical issues not identified in previous studies, support the development of new devices and therapies, and may facilitate reimbursement of the device components (and subsequent systems) in countries where they are not currently reimbursed.

J.2 Risks

Subjects participating in this study have a medical diagnosis of Type 1 diabetes requiring the daily use of insulin infusion or injections. There are risks inherent to Type 1 diabetes that are independent from their participation in the study:

- Hypoglycemia
- Severe Hypoglycemia
- Hyperglycemia
- Diabetic Ketoacidosis

The potential side effects related to the insulin administration and pump use, insulin pump infusion sets and finger sticks are anticipated to be the same as per standard of care for the study participants.

Standard risks associated with the medical device used in this clinical study and analyses of Adverse Device Effects are listed in the Instructions for Use or Investigator Brochure.

Possible interactions of the devices used in the study with concomitant medical treatments are not known.

The history of recall of the investigational devices is described in the Investigator Brochure, if applicable.

J.2.1 Potential risks associated with the use of the Enlite 3 Sensor

Serious Adverse Events during past studies involving glucose sensor use were relatively rare. Usually side effects are often limited to reactions to the sensor insertion site, adhesives or tape associated with device placement and device irritation on the skin. These potential risks include the following:

Skin irritation or reaction to adhesives, Bruising, Discomfort, Redness, Bleeding, Pain, Rash, Infection, Irritation from tapes used with glucose-sensing products, Raised bump, Appearance of a small "freckle-like" dot where needle was inserted, Allergic reaction, Fainting secondary to needle insertion, Soreness or tenderness, Swelling at insertion site, Sensor fracture, breakage or damage, Minimal blood splatter associated with sensor needle removal, Residual redness associated with adhesive and or tapes and Scarring.

Either the subject or investigational center may remove a sensor if they are concerned with skin irritation or skin discomfort. Also, the possibility of infection is minimized by aseptic technique of sensor insertion and site rotation. Subjects should base their diabetes management on fingerstick readings and not sensor glucose values.

While there is no evidence of an Enlite sensor breaking in a patient's body, if there is suspicion of sensor breakage, subject should contact his healthcare professional for assistance in removing the sensor.

The same risks apply for the subjects in the treatment arm and those in the control arm with the use of the GST3C transmitter device and sensor, with a reduced frequency of use for the control arm.

J.2.2 Potential risks associated with the use of the GST3C Transmitter

The GST3C transmitter is similar to the Guardian 2 Link transmitter which is CE-marked and commercially available.

There are no anticipated risks with the use of the GST3C at this stage.

Contra-indications:

Transmitter must not be exposed to MRI equipment, diathermy devices, or other devices that generate strong magnetic fields. If the transmitter is inadvertently exposed to a strong magnetic field, its use must be discontinued and it must be replaced.

J.2.3 Potential risks associated with the use of other investigational devices

No risks are known or anticipated at this stage with the other investigational study devices:

- GST3C Dock (T8381)
- GST3C Download Utility (9029393)

J.2.4 Potential risks associated with the use of MiniMed 640G Insulin pump:

Potential risks associated with the use of an insulin infusion pump include the risk of malfunction of the components of the system (pump, software, infusion set and reservoir) as well as the risk of use error during use of the system. Device deficiencies or use errors can result in administration of too much or too little insulin which can lead to the following clinical consequences:

- Hypoglycemia
- Hyperglycemia
- Diabetic ketoacidosis (DKA)
- Severe hypoglycemia with or without associated seizure, coma or death
- Kinked cannula leading to hyper or hypoglycemia
- Infusion set disconnection from pump leading to hypo or hyperglycemia
- Dislodged cannula leading to hypo or hyperglycemia
- A pump error indicating hardware failure may lead to under delivery
- Battery failure – no insulin delivered
- Remove a reservoir, without suspending and reconnecting after a while resulting in a

Hypoglycemia

- Insulin deterioration leading to hyperglycemia
- Incomplete priming; Fails to prime tubing and/or cannula, leading to hyperglycemia
- Remove a reservoir, without suspending and reconnecting after a while resulting in a

Hypoglycemia

- Patient not filling pump reservoir when needed leading to hyperglycemia
- Magnetic Resonance Imaging resulting in pump /Transmitter malfunction
- Inaccurate insulin delivery due to sudden altitude changes.
- Hypoglycemia or hyperglycemia from manual bolus
- Hypoglycemia or hyperglycemia from computer hacking

Risks associated with hyperglycemia include:

- DKA
- Symptomatic ketosis
- Cardiovascular event
- Dehydration
- Potassium and sodium imbalance
- Shock
- Altered mental status
- Coma
- Acidosis

Risks associated with hypoglycemia include:

- Seizure
- Coma
- Altered mental status
- Loss of consciousness
- Cardiovascular event
- Death
- Risk of rebound hyperglycemia with ketosis

Prevention and mitigation risks include:

- Investigational center staff and subjects will be instructed to follow the provided user guides for insulin pump management.
- Subjects will be trained prior to study device use and diabetes management principles and told to call with problems.
- Subjects will be required to check SMBG at least 4 times a day and before driving.
- Subjects will be told to have glucose on hand for hypoglycemia
- Subject with persistent hyperglycemia especially if ketones develop will be told they may need to change their infusion set if they suspect catheter occlusion or administer insulin with syringe.

Warning:

Exposure to magnetic fields and radiation: Pump must not be exposed to X-ray, MRI, diathermy treatment, CT scan, or other type of devices that generates radiation. The magnetic fields and radiation in the immediate vicinity of this equipment can make the device non-functional or damage the part of the pump that regulates insulin delivery, possibly resulting in over delivery and severe hypoglycemia.

The pump must not be exposed to a permanent magnet, such as pump cases that have a magnetic clasp. Exposure to a permanent magnet may interfere with the motor inside the pump.

This device complies with Industry Canada licence-exempt RSS standard(s). Operation is subject to the following two conditions: (1) this device may not cause interference, and (2) this device must accept any interference, including interference that may cause undesired operation of the device.

J.2.5 Potential risks associated with the use of SmartGuard Feature

- When SmartGuard is turned ON, the feature may not activate when the blood sugar is low.
- When SmartGuard is turned ON, the feature may falsely activate when the subject's blood sugar is not low.
- When SmartGuard is turned ON, it cannot always reduce the severity and duration of hypoglycemia (for example over-bolusing with insulin).
- Standard mitigations include:
- Subject instruction to test BG via finger stick testing > 4 times a day.
- Subject instruction to adhere to 100% sensor wear.
- Subject instruction to use the bolus wizard when determining meal or correction bolus.

J.2.6 Potential risks associated with the use of CONTOUR NEXT LINK 2.4 meter

The risks are not any different than the risk associated with the commercially available meters in Europe. For use of the meter, refer to the instructions for use.

All these risks must be continuously monitored, assessed and documented by the investigator in the *Adverse Event eCRF*.

J.3 Risk-to-benefit rationale

The results of risk analysis, balancing benefits against risks associated with both the device system itself and procedures involved in its use, is included in the Instructions for Use and Investigator's Brochure.

The present study devices are all used within their intended use.

Provided that patients will use the MiniMed 640G system as it is intended to be used in routine practice, the anticipated risks for a patient to be in the study is not expected to be higher than in routine practice in Europe.

The patients will be followed with higher frequency of visits, which will allow a closer medical follow-up when compared to standard of care.

With the use of continuous glucose monitoring by the patients in treatment group, it is anticipated to see a reduction of hypoglycemia. The risks associated with the use of the sensor as described in section J.2.1 are often limited to skin irritation. Serious Adverse Events that occurred in past studies involving the glucose sensor use were relatively rare. One goal of the run-in phase is to identify patients who would not tolerate sensor wear and therefore, they would not be eligible to be randomized into the study. As CGM is not reimbursed in all the participating countries, it can be a benefit for patients in the treatment arm to have access to this therapy within the course of the study.

K REFERENCES

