Null-hypothesis: $H_0: MNSHE_{TREATMENT} = MNSHE_{CONTROL}$

Alternative hypothesis: $H_A: MNSHE_{TREATMENT} \neq MNSHE_{CONTROL}$

The null-hypothesis will be rejected in favor of the alternative hypothesis if the p-value of the two-sided two-sample t-test is less than 0.05. Once the null hypothesis is rejected a nested superiority test in favor of the treatment group will be performed while maintaining the overall type 1 error.

C.4 Study population

Adults (aged 24-75 years) diagnosed with Type 1 Diabetes Mellitus with disease duration of 10 years or more before screening and currently on CSII therapy for at least 6 months will be enrolled. Subjects present an increased risk of hypoglycemia. Subjects can be naïve or experienced with the MiniMed 640G insulin pump, but should not have been on CGM therapy for at least 3 months prior to screening.

Sample size calculations have shown that 136 subjects (68 in each arm) need to complete the study (section C.7). Taking into account an anticipated drop-out rate of 10% at screening, 15% at run-in and 15% during the 6 month follow-up period, it is calculated that 210 subjects need to be screened, in order to have 189 subjects starting the run-in phase, and 160 randomized subjects.

Up to 25 study centers across Europe, Canada and potentially other geographic regions will be selected at study start, based on each investigator's experience and qualifications, availability of sufficient resources to carry out the required study procedures, and their potential to randomize an average of 9 subjects within the 6 month enrollment period. The number of investigational sites and period of enrollment may be increased to accommodate a quicker and/or larger enrollment.

C.5 Study design

This is an international, multi-center, prospective, open-label, adaptive, randomized, controlled, pre-market clinical investigation with parallel groups. The study is designed to compare CGM-based hypoglycemic events in a treatment group to a control group. Groups are defined as:

- Treatment group: CSII with MiniMed 640G with CGM and Suspend before Low feature of SmartGuard turned ON (T)
- Control group: CSII with MiniMed 640G alone (C)

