This study has an adaptive design. Due to the uncertainty about the hypoglycemic event rate and the magnitude of the true effect of treatment, the sample size will be re-estimated by Data Safety Monitoring Board (DSMB) in an interim assessment after a total of 60 subjects (30 treatment and 30 control group) have been randomized and followed up for 6 months. An interim analysis for sample size re-estimation will be based on the conditional power approach by Li et al. [17] and a method of by Chen et al. [18] as extended by Mehta and Pocock [19].

The interim analysis will be performed by a statistician unaffiliated with the sponsor or study statistician and member of the DSMB. Detailed instructions will be given to this statistician concerning the analysis, because it involves both the primary safety and efficacy endpoints.

The DSMB will share no data or results of analyses with the sponsor or sponsor's statistician, and present one of following messages to the sponsor after the interim analysis:

- Study has reached the futility boundary and it is recommended to be terminated for futility.
- Continue the study to its conclusion without modification of sample size or inclusion criteria.
- Increase the numbers of patients in each treatment group.
- Revise the inclusion criteria.

The statistician will prepare and save a report of the interim analysis. This report will be sent to the sponsor on completion of the study.

C.6 Randomization

The randomization will follow a block randomization with blocks of different sizes. At site level, the order of the block sizes will be selected randomly and a random 1:1 treatment allocation will be performed within each block.

Investigators will be blinded to the number and size of the blocks.

Randomization will be performed via the electronic CRF.

In case technical issues occur with the electronic CRF (i.e. Internet access, system maintenance), a randomization list will be generated for each site by the statistician and the statistician will be able to communicate the randomization arm to the study team and site staff.

C.7 Sample size

The sample size calculation was performed based on assumptions from the results from the *ASPIRE* study [3]. In particular, the mean number of sensor glucose hypoglycemic events below or equal to 55 mg/dL (3.0 mmol/L) per patient/week is expected to be 2 in the arm with CSII with MiniMed 640G alone (control group) and standard deviation of 1.56.

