Assuming alpha=0.05, power=80% and 40% reduction in the mean number of sensor glucose hypoglycaemic events per patient/week in the treatment arm, as compared to the control arm, the required sample size is 136 subjects (68 in each arm).

The drop-out rate during the 6 month follow-up after randomization has been estimated to be 15%. Incorporating this drop-out rate, a total of 160 subjects will be randomized in a 1:1 ratio to either the arm using MiniMed 640G with CGM and SmartGuard or the arm using CSII with MiniMed 640G alone.

The following drop-out assumptions have been taken into account, based on experience with previous studies:

- At screening: 10%
- After run-in: 15%
- During 6 months follow-up: 15%

Based on these assumptions, the following estimations can be made: in total 210 subjects need to be screened, in order to have 189 starting the run-in phase and 160 randomized to start the treatment phase.

Due to the uncertainty about the magnitude of the effect of treatment, the sample size will be re-estimated by the independent DSMB in an interim assessment soon after a total of 60 subjects (30 treatment and 30 control group) have been randomized and followed up for 6 months.

Enrollment period is expected to be 6 months. It may be extended based on the outcome of the interim analyses.

C.8 Number of investigational sites and study duration

The study is planned to be conducted in Europe in the following countries: Netherlands, France, Italy, and the UK, where the MiniMed 640G system is commercially available. The study will also be conducted in Canada, where the MiniMed 640G system is not licensed and therefore will be investigational. Other geographic regions are also being considered. At the time this Clinical Investigation Plan was finalized, not all participating investigation sites were identified. A list of participating investigation sites will be available under a separate cover.

It is estimated that 205 subjects will have to be enrolled in up to 25 study centers, which will be activated over a period of 6 months (see also section C.7).

The recruitment period will be 6 months, but could be extended if needed. At the finalization of this document, recruitment of 11 subjects on average at each site is expected.

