6.2. Sample size

The sample size calculation was performed based on assumptions from the results of the *ASPIRE study* (Bergenstal, et al., 2013). In particular, the mean number of sensor glucose hypoglycemic events below or equal to 55 mg/dL (3.0 mmol/L) per subject/week is expected to be 2 with standard deviation of 1.65 in the Control arm (CSII therapy alone with MiniMed 640G).

Assuming a two-sided two-sample t-test, alpha=0.05, power=80% and 40% reduction in the mean number of sensor glucose hypoglycemic events per subject/week in the Treatment arm (SAP with MiniMed 640G and SmartGuard), as compared to the control arm, the required sample size is 136 subjects (68 in each arm) completing the 6 month follow up of the study phase.

The dropout rate during the 6-month follow-up after randomization has been estimated to be around 15%. Incorporating this dropout rate, a total of 160 subjects will be randomized in a 1:1 ratio either to the SAP therapy arm (MiniMed 640G with SmartGuard) or to the CSII therapy arm (MiniMed 640G).

7. Statistical Methods

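### Protocol C.7's planning SD of 1.56 does not give its stated 68 per arm at 80% power; SAP 6.2 cites the same source with SD 1.65, which does

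*Protocol*

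**What the plan says.** Protocol C.7 takes its assumptions from a cited earlier trial (reference [3]). The control-arm rate of sensor hypoglycaemic events per patient per week "is expected to be 2 in the arm with CSII with MiniMed 640G alone (control group) and standard deviation of 1.56". It continues: "Assuming alpha=0.05, power=80% and 40% reduction in the mean number of sensor glucose hypoglycaemic events per patient/week in the treatment arm", and concludes that "the required sample size is 136 subjects (68 in each arm"). Allowing for 15% drop-out, 160 are to be randomised 1:1. Protocol C.3 names the test: the null hypothesis is rejected "if the p-value of the two-sided two-sample t-test is less than 0.05".

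SAP 6.2 refers to the same publication, but there the rate "is expected to be 2 with standard deviation of 1.65 in the Control arm". The remaining inputs are those of the protocol: "Assuming a two-sided two-sample t-test, alpha=0.05, power=80% and 40% reduction in the mean number of sensor glucose hypoglycemic events per subject/week". So is the result: "the required sample size is 136 subjects (68 in each arm) completing the 6 month follow up of the study phase", with 160 randomised after about 15% drop-out.

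SAP 7.12 lists the changes from the protocol and the reasons for them. The SD is not among them.

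**The concern.** The two SDs have the same digits with the last two exchanged, and everything around them is identical. Two different SDs cannot both lead to 68 per arm at 80% power when the mean, reduction, alpha and test are the same, so at least one document's calculation cannot be internally consistent. Because SAP 7.12 is silent, the difference cannot be read as a declared update.

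At stake is the justification of the primary sample size in the governing protocol. As C.7 stands, either its SD or its stated power is wrong, and anyone who checks the calculation from the protocol alone will fail to reproduce it. Enrolment and the planned analysis are not at stake.

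**Working it through.** **Inputs**

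- Control mean 2 events per week; 40% reduction, so treatment mean 1.2 and δ = 0.4 × 2 = 0.8 (Protocol C.7, SAP 6.2)
- SD 1.56 (Protocol C.7) or 1.65 (SAP 6.2)
- Two-sided alpha 0.05, two-sample t-test (Protocol C.3, SAP 6.2); power 80%; 1:1 allocation
- Assumption: the control-arm SD applies to both arms, since neither document gives a treatment-arm SD

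**Formula**

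The normal approximation is n per arm = 2 × [SD × (z₀.₉₇₅ + z₀.₈₀) / δ]², with z₀.₉₇₅ + z₀.₈₀ = 1.960 + 0.842 = 2.802. The exact t-test calculation (noncentral t) adds about one subject per arm.

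**The plan's figure, using the SAP's SD of 1.65**

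- Normal: 2 × (1.65 × 2.802 / 0.8)² = 66.8, so 67 per arm
- t-test: 67.75, so **68 per arm**, 136 in total. This matches.
- 136 / 0.85 = 160 randomised. This matches.

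**The same calculation with the protocol's SD of 1.56**

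- Normal: 2 × (1.56 × 2.802 / 0.8)² = 59.7, so 60 per arm
- t-test: 60.67, so **61 per arm**, 122 in total. This does not match 68.
- 122 / 0.85 = 143.5, so 144 randomised. This does not match 160.

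**What 68 per arm delivers under each SD (t-test)**

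| | SD 1.56 | SD 1.65 |
|---|---|---|
| Required n per arm at 80% power | 61 | 68 |
| Power at 68 per arm for δ = 0.8 | 84.3% | 80.1% |
| Difference detectable at 80% power, 68 per arm | 0.755 | 0.799 |
| The same as a reduction from 2 | 37.7% | 39.9% |

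**Which SDs give 68?** With 68 per arm and 80% power the detectable standardised difference is 0.4839; with 67 per arm it is 0.4876. The SD must therefore lie between 0.8 / 0.4876 = 1.641 and 0.8 / 0.4839 = 1.653. To two decimals only 1.65 qualifies: 1.64 gives 67 and 1.66 gives 69.

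**Does another reading rescue 1.56?**

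- One-sided alpha 0.05: 48 per arm.
- A smaller treatment-arm SD, scaled by 0.6 or √0.6 in line with the lower mean: 42 or 49 per arm by t-test.
- A larger treatment-arm SD: to reach 68, the average of the two variances must equal that of a common SD of 1.641 to 1.653. The treatment-arm SD would then be √(2 × 1.641² − 1.56²) to √(2 × 1.653² − 1.56²), about 1.72 to 1.74. That is above the control SD despite a mean of 1.2, and neither document says so.
- 85% power: 70 by t-test, 69 by normal approximation. Both documents state 80%.
- Drop-out already included in the 68: no, because both documents treat 136 as completers and inflate afterwards to 160.

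**The case against.** The best case against giving this much weight is that nothing operational depends on it. If 1.65 is right, 68 per arm is exact; if 1.56 is right, 68 exceeds the 61 needed. Both documents state 80% power, SAP 6.2 supplies a full set of inputs that reproduces 68, and 84% appears nowhere. The natural reading is therefore that the trial was planned at 80% with 1.65 and that two digits were exchanged in the protocol. Protocol H.1 has the interim re-estimation use the observed effect and the estimated SD, so nothing in these documents carries the planning SD forward. A protocol correction also has a procedural price: under F.8.3 even administrative amendments are notified to the ethics committees and signed by investigators.

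Most of this stands as a statement about consequences. It is fair that the internal evidence favours 1.65, and that the visible text does not show the planning SD entering the interim. It does not remove the error. C.7 is the stated basis for the primary sample size, its figures do not agree with one another, and SAP 7.12 gives no explanation. The transposition is an inference: the source publication is not among the documents, so the possibility that it reports 1.56 is open. The amendment burden bears on when to make the correction, not on whether to make it.

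**Conclusion.** The point holds. Protocol C.7's inputs give 61 per arm, not 68, a gap of 7 per arm or 14 in total. If its SD is kept, 68 per arm corresponds to 84.3% power rather than 80%. SAP 6.2's SD of 1.65 reproduces 68 per arm, 80.1% power and 160 randomised.

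This rests on the t-test named in both documents and on one SD common to the arms. The powers are planning values for that test, not the power of the baseline-adjusted mixed model in SAP 7.9.1. It does not establish which SD the source study reports. The error should be corrected because it sits in the primary sample-size justification, but the planned size is adequate for the stated effect under either SD.

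**What to change.** Check the SD against the cited source study, then do one of the following:

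- **If it is 1.65:** correct the SD in Protocol C.7. Nothing else changes.
- **If it is 1.56:** keep 136 completers and 160 randomised, put 1.56 in SAP 6.2, and restate the power at 68 per arm as about 84% in both documents.

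In either case, record the correction, for example in SAP 7.12. It would also help to add a few words in both places saying that the SD is assumed common to the two arms. Confirm that the separate DMC analysis plan, which is not available here, uses the same value if it quotes a planning SD.

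The cost is one source check and one figure, or one SD and two power statements. Because no procedure changes, the protocol edit can be carried with the next amendment to limit the notification and signature work under F.8.3. Sample size, recruitment and analysis stay as they are.
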